#### Safety Analyses

All patients randomized to treatment who receive at least one dose of double-blind study drug will be included in the safety analyses. Summary statistics will be provided for all safety data using appropriate descriptive statistics adverse events, Sheehan-STS, laboratory tests, ECGs, vital signs, AIMS, BARS, and SAS.

For QTcF, an ANCOVA model by assessment times (visit and timepoint within visit) using the change from baseline (as dependent variable) with treatment arm (MIN-101 32 mg, MIN-101 64 mg, and placebo) as a factor, and Baseline value as covariate. Estimates for the difference at each assessment time for each dose group versus placebo, standard error of the mean, and the upper bound of the 2-sided 90% confidence intervals will be presented.

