## Pharmacokinetic / Pharmacodynamic Analyses

The effect of coincidentally measured (time-matched) plasma concentrations of MIN-101 and BFB-520 as compared to placebo on QTcF changes from Baseline will be analyzed utilizing the plasma concentration bin method. This analysis will pool all assessment times at which both the QTcF and PK data are available and will treat the bins as separate groups using quartile distribution. Plasma concentration data from placebo-treated patients will be set to 0 (zero). Repeated measures ANCOVA model will be used and will include PK concentration Bin Group and per-protocol assessment times as fixed effects, Baseline QTcF as a covariate, and patient nested in treatment as a random effect.

Furthermore, the analysis will be repeated by using the largest QTcF increase value (worst case) per patient, with the matched plasma concentration level independent of time of assessment, will also be performed using ANCOVA model with PK concentration Bin Group as fixed effects, Baseline QTcF as a covariate, and patient nested in treatment as a random effect. Analysis of the largest time-matched mean difference from Baseline will also be explored, as applicable.

P-value and the least squares means difference, and the corresponding upper bound of the two-sided 90% confidence intervals for the change from baseline versus placebo will be computed for each bin.

These analyses will be performed for MIN-101 plasma concentration and its main metabolites, as separate analyses.

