Thorough review of safety information relevant to the use of MIN-101 indicates that MIN-101 is generally safe and well tolerated, with the most frequently reported TEAEs being headache, anxiety, asthenia, and insomnia in patients with schizophrenia. None of the "classical" side effects generally associated with the currently marketed typical or atypical antipsychotic treatments were observed, such as sedation, prolactin and weight gain increases, or extrapyramidal symptoms. QT prolongation was observed in clinical trials with MIN-101. The risk for QT prolongation is dose related, the main driver for QT prolongation being BFB-520 plasma levels. In the MIN-101C03, 2 patients receiving the highest dose (64 mg) of MIN-101 MR formulation, presented with a significant increase in QTcF. These 2 patients were found to be outliers for BFB-520 levels and were identified within the first 4 weeks of treatment.

To mitigate the risks of antipsychotic discontinuation, patients who entered this trial will be closely followed by the treating/research team by frequent face to face visits and phone calls between visits. This will enable the treatment/research team to intervene promptly as soon as patients experience symptomatic worsening or display behaviors that endanger themselves or others.

To mitigate the risk for QT prolongation, a new formulation will be used in the present study that was developed to specifically avoid the presence of high levels of drug and metabolite concentrations while resulting in the same bioavailability (AUC) observed with the formulation used in the Phase 2b study, which resulted in positive treatment effect.

The following measures have also been implemented in the protocol to further mitigate the risk for QT prolongation:

- Only CYP 2D6 extensive metabolizer patients, will be enrolled.
- Drugs likely to increase QT as well as drugs inhibiting CYP 2D6 and CYP3A4/5 (likely to increase MIN-101 and BFB-520 levels) are not allowed during study participation.
- Exclusion of patients with known personal or familial history of QT prolongation (including congenital long QT syndrome), or with recent acute myocardial infraction, or with uncompensated heart failure.
- Exclusion of patients presenting with risk factors such as hypokalemia, hypomagnesemia, hypocalcemia or bradycardia.
- Close monitoring of the patients, who will be hospitalized during the first 2 days of treatment.

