# 9.3. Stopping Rules

In addition, specific stopping rule criteria for a patient's withdrawal are described below:

- 1. Increase from Baseline in PANSS total score of 25% and an increase of 3 points or more on the hallucinations, suspiciousness/paranoia, hostility, delusions, or uncooperativeness PANSS items.
- 2. CGI-S worsening of more than 2 points.
- 3. Suicidal ideations or behavior.
- 4. Occurrence of an AE, which may jeopardize the patient's health as per investigator opinion.

- 5. Worsening of psychotic symptoms or occurrence of any dangerous behavior against self or others as per investigator opinion.
- 6. Patient with significant increase in ALT (i.e., > 5 ULN).
- 7. Patient with abnormal laboratory results with simultaneous increases of total bilirubin (> 2 ULN), ALT or AST (> 3 ULN) with alkaline phosphatases (< 1.5 ULN).
- 8. Patient with sustained mean QTcF value > 500 msec (confirmed by a second ECG under strict resting position and at minimum at ½ hour [30 minutes] duration from the first measurement). Patient's treatment must be discontinued until mean QTcF values are obtained from the ECG central-reader. If values are confirmed, the patient must be discontinued from the study, else treatment is restarted at the discretion of the investigator.
- 9. Patient with sustained mean increase of > 60 msec in the QTcF compared to Baseline (confirmed by a second ECG under strict resting position and at minimum at ½ hour [30 minutes] duration from the first measurement). Patient's treatment must be discontinued until mean QTcF values are obtained from the ECG central-reader. If values are confirmed, the patient must be discontinued from the study, else treatment is restarted at the discretion of the investigator.
- 10. If the patient for any reason requires treatment with another therapeutic agent that has been demonstrated to increase the QT interval or inhibit CYP 2D6 or CYP 3A4. In this case, discontinuation from the study occurs prior to introduction of the new agent.
- 11. If the patient experiences a syncope or dizziness not explained by other known causes, such as documented orthostatic hypotension, Ménière disease, etc.
- 12. Patient has an overt seizure or reports seizure-like activity (loss of consciousness, uncontrollable tremor not due to EPS). A seizure or seizure like activity will be followed-up on-site using SAE follow-up forms, neurological examination, and EEG monitoring.

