#### 5.4.5. ECG Assessments

ECG measurements will be provided by a central reader.

ECGs are recorded in triplicate one minute apart, and all ECG analyses will be based on the average of triplicate measurements. The mean of the 3 triplicates (9 assessments) performed on Day -1 will be used as the Baseline for all analyses of that safety parameter.

ECG variables and their change from Baseline will be summarized with descriptive statistics by time point and treatment group. ECG variables will include heart rate, PR interval, RR interval, QRS interval, QT interval, and QTc interval corrected for heart rate using Fridericia's correction, QTcF.

QTcF values will also be tabulated for their absolute values and tabulated relative to Baseline measurements in order to detect individual QTcF changes. Additionally, the number and percentage of patients who meet the PCS values defined in Table 6 will be summarized.

Table 6 Criteria for Potentially Clinically Significant ECG Parameters

			Criteria
Parameter	Flag Observed Value		Change from Baseline or Observed Value
Heart Data (hous)	High	> 110	
Heart Rate (bpm)	Low	≤ 50	
QTcF a Interval (msec)	High Male	> 450	>30-60, > 60, > 450-480,
Q'Tel' Interval (insee)	High Female	> 470	> 480-500, > 500
QRS Interval (msec)	High	> 120	
PR Interval (msec)	High	> 220	

<sup>a QTc interval is derived as: QTcF=QT Interval (msec) / (RR (msec)/1000)(1/3)

To understand the effect of treatment arm on the change in QTcF, an ANCOVA will be performed by assessment times (visit and timepoint within visit) using the change from Baseline (as dependent variable) with treatment arm (MIN-101 32 mg, MIN-101 64 mg, and placebo) as a factor, and Baseline value as covariate. Estimates for the difference at each assessment time for each dose group versus placebo, standard error of the mean, and the upper bound of the 2-sided 90% confidence intervals will be presented.

Important abnormalities in ECG waveform that are changes from Baseline readings will also be reported in a listing, as well as PCS ECG parameters.

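### The separate QTcF ANCOVA at each time can modestly understate the later 64 mg effect, because patients stopped for QTcF supply no further on-treatment ECGs

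*Protocol*

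**What the plan says.** **The comparison.** The protocol synopsis plans "an ANCOVA model by assessment times (visit and timepoint within visit) using the change from baseline (as dependent variable) with treatment arm" as a factor and Baseline as covariate. SAP 5.4.5 likewise states that "an ANCOVA will be performed by assessment times (visit and timepoint within visit) using the change from Baseline (as dependent variable) with treatment arm" as a factor and Baseline as covariate. Protocol 10.8.4 has the same model. It has no patient effect and no link between times. For each dose against placebo, "the upper bound of the 2-sided 90% confidence intervals will be presented".

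**Missing data.** SAP 3.3.4.1 specifies imputation for the Week 12 NSFS and PSP only. Nothing is specified for QTcF.

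**The stopping rules.** Protocol 9.3 lists, as rule 8, "Patient with sustained mean QTcF value > 500 msec" and, as rule 9, "Patient with sustained mean increase of > 60 msec in the QTcF compared to Baseline". Treatment is held until the central reader's values arrive, and a confirmed case leaves the study.

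**Where such cases were seen.** Protocol 1.4.2.3 places every earlier patient-study case of QTc above 480 msec or a rise above 60 msec at 64 mg. Protocol 1.5 reports that in Phase 2b "2 patients receiving the highest dose (64 mg) of MIN-101 MR formulation, presented with a significant increase in QTcF", both found within the first 4 weeks.

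**Termination ECGs.** Early terminators have the Visit 11 procedures (Protocol 8.1.3.4), which include an ECG. In SAP 3.3.7, the Week 12 row of Table 1 takes in the termination visit, and a footnote applies that row to ECG tables. The text above the table instead slots early-termination assessments into day windows like any other assessment.

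**Other QTcF analyses.** Threshold counts are planned in Protocol 10.8.4 and SAP Table 6. The protocol also plans a concentration-bin model ("Repeated measures ANCOVA model will be used and will include PK concentration Bin Group and per-protocol assessment times as fixed effects") and a worst-case-per-patient version. SAP section 7 moves that PK/PD work to the population PK report, and SAP 5.3.2 now models efficacy scales only.

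**The concern.** A patient who meets rule 8 or 9 counts at the visit that triggered the rule and then has no scheduled on-treatment ECG. The patients lost this way are selected for a high QTcF and are expected mainly in one arm. At later visits the 64 mg mean is then taken over patients who did not have the large response, while placebo is hardly affected. The difference is pulled down, and the 90% upper bound with it.

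The values that caused the withdrawal are in the database. A likelihood-based repeated-measures model would use them when estimating later means; separate ANCOVAs ignore them. The plan already uses such models for NSFS and PSP, and in the protocol for binned QTcF. After the move described in SAP section 7, the per-time ANCOVA is the SAP's only model-based QTcF comparison of the randomised arms.

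**Working it through.** **Plan's own figures.** The documents give no SD, margin or sample size for QTcF. The only sample size is for NSFS, and it reproduces: a 3-point difference, SD 6.5, two-sided 0.05 and 90% power need 99 per arm (99.6 with the t distribution, so 100); 100/0.60 = 167; 167 × 3 = 501. It serves below only to scale precision.

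**Inputs from the documents.** Phase 2b randomised 244 and 165 completed 12 weeks (Protocol Table 2), so 79/244 = 32.4% dropped out. Two 64 mg patients had a significant QTcF increase (Protocol 1.5).

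**Assumptions.** Equal Phase 2b arms, 244/3 = 81.3, giving an outlier fraction f = 2/81.3 = 2.46%. Mean change in withdrawn patients +61 to +80 msec; in remaining 64 mg patients +5 to +10 msec. The documents give none of these, nor the QTcF SDs used below.

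**Step 1: direct arithmetic.** If a fraction f is removed,

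bias in the later 64 mg mean = −f × (mean of withdrawn − mean of remaining).

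| f | smallest | largest |
|---|---|---|
| 1% | −0.01 × (61 − 10) = −0.5 | −0.01 × (80 − 5) = −0.75 |
| 2.46% | −0.0246 × (61 − 10) = −1.25 | −0.0246 × (80 − 5) = −1.84 |
| 5% | −0.05 × (61 − 10) = −2.55 | −0.05 × (80 − 5) = −3.75 |

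**Step 2: simulation of the rule.** Six visits, leaving after a confirmed change above 60 msec, within-patient SD 10 msec. The bias is zero at the first visit and grows. At the last visit it is:
- no outlier subgroup, between-patient SD 10 to 20: −0.02 to −0.83 msec;
- 2.46% outliers near +65 to +80, between-patient SD 15: −1.48 to −1.95 msec;
- 5% outliers near +70, between-patient SD 15: −3.14 msec.

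**Step 3: what a repeated-measures model recovers.** With 2.46% outliers near +70, between-patient SD 15 and residual SD 10, the last-visit 64 mg mean is 11.48 with full data, 9.66 among patients still observed (−1.82) and 11.12 from the repeated-measures likelihood (−0.36).

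A second simulation used 167 per arm, 32% other drop-out, a mean effect of 8 msec at 64 mg and outliers near +62. Last-visit differences from placebo:

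| Outliers | Patient SD / residual SD | True | Per-time | Repeated measures |
|---|---|---|---|---|
| 2.5% | 9 / 8 | 9.3 | 8.2 | 8.9 |
| 5% | 9 / 8 | 10.8 | 8.3 | 10.0 |
| 2.5% | 6 / 10 | 9.3 | 8.1 | 8.5 |

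The last row shows the limit. When visits are weakly correlated, most of the bias remains (−0.8 of −1.2 msec).

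**Step 4: Week 12 and the termination ECG.** A patient stopped on Day 20 falls in Week 3 under the day windows (Days 19 to 25) and in Week 12 under the termination row.
- Counted in Week 12 and still on drug: the step 2 bias becomes +0.02 to +0.37 msec.
- Counted in Week 12 but off drug, with QTcF back at Baseline: bias = f × (0 − mean of withdrawn) = −0.0246 × 61 = −1.50 to −0.0246 × 80 = −1.97 msec, worse than leaving it out.

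**Scale.** The 90% half-width at 100 per arm is 1.645 × SD × √(2/100): 2.3 msec for SD 10 and 4.7 msec for SD 20. The largest mean QTcF change in the Phase 2a study was 11.7 msec (Protocol 1.4.2.3).

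**The case against.** A reader might infer that stopped patients vanish from every later comparison. The SAP does not support that. The triggering ECG counts at its own time, and Table 1 places the termination visit in the Week 12 ECG summary. What remains is narrower: Weeks 2 to 8 gain nothing from the Week 12 row, the general windowing rule points elsewhere, and an ECG taken after treatment is held may show little drug effect.

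A reader might also take this ANCOVA for the main QT result of the trial. No section gives it that rank, a margin or a sample size. The threshold counts keep extreme responders visible, and the concentration-bin and worst-case analyses were moved rather than deleted. That stands. But counts do not correct a mean difference or its upper bound, and the moved analyses are outside this SAP.

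The size is fairly challenged. The text available for this review does not say how large the two Phase 2b increases were or whether those patients were stopped. The new formulation lowers Cmax (test-to-reference ratios 0.66 for MIN-101 and 0.74 for BFB-520; Protocol 3.2), so 2.5% may be too high. The bias is also smaller than the 90% half-width.

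Finally, the documents define no QT estimand. The repeated-measures estimate addresses the effect had stopped patients stayed on drug; the ANCOVA describes those still observed. Both can be reported, but the second is no longer a comparison of the groups as randomised.

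**Conclusion.** The concern holds in a limited form. At visits after QTcF-rule withdrawals, the 64 mg versus placebo difference and its 90% upper bound can be understated. The amount is about 1 to 2 msec at a Phase 2b-like outlier rate of 2.5%, and about 2.5 to 3.8 msec at 5%. It is near zero for 32 mg, where no earlier case above 60 msec is reported, and near zero at 64 mg if the reformulation removes the outliers. The first post-dose comparisons are unaffected. The direction follows from the design; the size rests on assumed QTcF SDs, outlier means and Phase 2b arm size. At Week 12 even the direction depends on which termination-ECG rule is applied and whether that ECG is on drug. This is a worthwhile, inexpensive improvement. It does not show that the planned QT evaluation fails.

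**What to change.** - In the synopsis, Protocol 10.8.4 and SAP 5.4.5, estimate the same per-time differences and 90% upper bounds from one likelihood-based repeated-measures model on on-treatment QTcF changes. Terms: treatment, assessment time, treatment-by-time, Baseline QTcF and region. Model within-patient correlation with patient and patient-within-visit effects, or an unstructured matrix across visits.
- Keep the per-time ANCOVA as a sensitivity analysis.
- In SAP 3.3.7, reconcile the Table 1 termination row with the day-window rule, and define on-treatment for ECGs so that off-drug recordings do not enter as on-treatment Week 12 values. The new model needs this too, since off-drug values would bias it as well.
- Tabulate withdrawals under rules 8 and 9 by arm and visit.

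Cost: SAP and protocol wording and modest programming, with no new data. The model adds a covariance assumption, which the retained ANCOVA helps to check, and it reduces the bias without eliminating it.

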## Pharmacokinetic / Pharmacodynamic Analyses

The effect of coincidentally measured (time-matched) plasma concentrations of MIN-101 and BFB-520 as compared to placebo on QTcF changes from Baseline will be analyzed utilizing the plasma concentration bin method. This analysis will pool all assessment times at which both the QTcF and PK data are available and will treat the bins as separate groups using quartile distribution. Plasma concentration data from placebo-treated patients will be set to 0 (zero). Repeated measures ANCOVA model will be used and will include PK concentration Bin Group and per-protocol assessment times as fixed effects, Baseline QTcF as a covariate, and patient nested in treatment as a random effect.

Furthermore, the analysis will be repeated by using the largest QTcF increase value (worst case) per patient, with the matched plasma concentration level independent of time of assessment, will also be performed using ANCOVA model with PK concentration Bin Group as fixed effects, Baseline QTcF as a covariate, and patient nested in treatment as a random effect. Analysis of the largest time-matched mean difference from Baseline will also be explored, as applicable.

P-value and the least squares means difference, and the corresponding upper bound of the two-sided 90% confidence intervals for the change from baseline versus placebo will be computed for each bin.

These analyses will be performed for MIN-101 plasma concentration and its main metabolites, as separate analyses.

## **Extension Phase**

Patients enrolled in the 40-week open-label extension phase will receive either MIN-101 64 mg or 32 mg. Patients who received placebo in the double-blind 12-week treatment phase will receive one of the 2 MIN-101 doses according to the randomization schedule used at the beginning of the double-blind phase (Day 1). Data from all patients enrolled in the 40-week extension phase will be summarized descriptively, as appropriate, by treatment arm sequence (MIN-101 64 mg, MIN-101 32 mg, placebo to MIN-101 64 mg, placebo to MIN-101 32 mg, overall MIN-101, overall placebo to MIN-101, and overall) as appropriate, and by visit.

# DSMB

An external DSMB will be established to review the safety data and formulate recommended decisions/actions in accordance with the charter of the DSMB. The DSMB will consist of 2 clinicians (psychiatrist and cardiologist), and a statistician, one of whom will chair the board. The DSMB will review the outputs from statistical summaries of demographics and safety data prepared by the contract research organization managing the study on behalf of the sponsor who are not otherwise affiliated by the study team.

Further details regarding the safety analysis will be specified in a separate DSMB charter.

#### TIME AND EVENTS SCHEDULE – DOUBLE-BLIND PHASE

Study Phase	3- to 4-W	3- to 4-Week Pre-Treatment Phase				Double-Blind Treatment Phase						
	Screening Period	Washout Period	Baseline									
Study Day/Week a	Day -28 to Day -2	Day -2	Day -1	Day 1	Day 2	Week 1	Week 2	Week 3	Week 4	Week 8	Week 12 m	
Visit Number	1	2	3	4	5	6	7	8	9	10	11	
Procedures												
Informed consent	X											
Patient demography	Х											
Psychiatric and medical history	X											
MINI	Х											
Prior medication	X	Х										
Urine drug screen	X	X										
Inclusion/exclusion criteria	X	X	Х									
Hospitalization b			Continuo	us	5 20	Xb	Xb				Х	
Randomization				X								
Safety Assessments												
Vital signs c	X		X	X	X	X	X	X	X	X	Х	
Height/weight/waist circumference d	X		Х						X	X	X	
Physical examination	Х		Х						X		Х	
12-lead ECG (triplicate)e	X		Х	X	X	X	X	Х	X	X	Х	
Safety laboratories f	Х	Х							X	X	Х	
HbA1c laboratory test	Х		Х								Х	
Serology (HBsAg, HCV, and HIV)	X											
Urinalysis g	X		Х						X	X	Х	
Pregnancy test h	Х	X							X	X	X	
RDQ i					X							

Study Phase	3- to 4-W	Double-Blind Treatment Phase									
	Screening Period	Washout Period	Baseline								
Study Day/Week a	Day -28 to Day -2	Day -2	Day -1	Day 1	Day 2	Week 1	Week 2	Week 3	Week 4	Week 8	Week 12 m
Visit Number	1	2	3	4	5	6	7	8	9	10	11
AIMS	х		Х						Х	X	X
SAS and BARS	x		X			X	X	X	X	X	X
Safety Assessments (Cont'd)											
Sheehan-STS	Х		X	X	X	X	X	X	X	X	X
Adverse events					Conti	nuous	· · · · ·	ι			
Concomitant medication					Conti	nuous					
Other Laboratory Assessments											
CYP 2D6 genotyping	X										
Pharmacokinetic and concomitant medications sampling j				X	X	X	X	Х	Х	X	X
Efficacy Assessments											
	X		X				X		Х	X	X
PSP			X						X	X	X
CGI-S	X		X				X		X	X	X
							X		X	X	Х
			X						X		X
	X		Х						Х	X	X
Study Medication											
Administration				X	X	X	Х	Х	X	X	X
Dispense study drug k					X	X	Х	X	X	X	
Study drug accountability 						Х	Х	Х	X	X	X

NOTE: Patient's eligibility must be verified, including Baseline laboratory results, before the patient can be randomized.

**NOTE:** Weeks 2 to 12 (Visits 7 to 13) have  $\pm 2$  days window.

**NOTE:** Patients to be contacted via phone at Weeks 5, 6, 7, 9, 10, and 11 to verify safety and to make sure the patient is doing well and is compliant with study medication. **Abbreviations:** AIMS = Abnormal Involuntary Movement Scale; BARS = Barnes Akathisia Scale;

CGI-S = Clinical Global Impression-Severity Scale; CYP = cytochrome; ECG = electrocardiogram; EOS = end-of-study; HbA1c = hemoglobin A1c; HBsAg = surface antigen of hepatitis B virus; HCV = hepatitis C virus; HIV = human immunodeficiency virus; MINI = Mini International Neuropsychiatric Interview; PANSS = Positive and Negative Syndrome Scale; PSP = Personal and Social Performance; RDQ = Readiness for Discharge Questionnaire; SAS = Simpson-Angus Scale; STS = Suicidality Tracking Scale.

Footnotes:

- a Visits 7 to 13 may occur  $\pm$  2 days from scheduled visit.
- b Visits 2-5 hospitalization may be extended at the discretion of the investigator. Hospitalization on Visits 6 and 7 are at the discretion of the investigator to ensure per-protocol ECG assessment and PK sampling are done. Hospitalization includes admission to a hospital or the utilization of an inpatient facility.
- c Vital signs (blood pressure, heart rate, respiratory rate, and oral or aural body temperature) obtained after the patient is resting in supine position for ≥ 5 minutes. Vital signs during hospitalization are assessed pre-dose within 30 minutes of dosing, and at about 4 hours post dosing. All other assessments are at about 4 hours post dosing.
- d Height only at Screening Visit; Patients will be weighed clothed (lightly) and without shoes at every indicated visit.
- e Scheduled ECG recordings (in triplicate) should be obtained after the patient is resting in supine position for ≥ 10 minutes. Three triplicate ECG assessments (9 assessments) should be performed on Day -1 to serve as the Baseline value. Scheduled ECG recording during hospitalization (Visits 4 through 7 and Visit 11) should be done prior to the planned PK sample at pre-dose within 30 minutes of dosing, and at the approximate time of maximum plasma concentration of both MIN-101 (6 to 8 hours post dosing) and BFB-520 (9 to 12 hours post dosing). Scheduled ECG recordings on Visits 8 to 10 should be done prior to the planned PK sample 2-4 hours post dosing after all other assessments have been completed.
- f Safety laboratory tests include haematology, serum chemistry (including serum lipid profile, and fasting blood glucose) and prolactin. Patients must fast for 8 hours before the blood sample is taken. Baseline safety laboratory tests will be performed no later than Day -2 (and not earlier than Day -5) to ensure results are available prior to the first study drug administration.
- g Dipstick urinalysis will be completed on site at Screening, Baseline, and Weeks 4, 8, 12 (or early termination). Urine specimen will only be sent to the central laboratory for microscopic analysis in the event the dipstick results are abnormal.
- h All females of childbearing potential will have a serum pregnancy test at Screening and Week 12 / Visit 11 (or in case of early termination); urine samples will be collected at Baseline (Day-2) and Visits 9, 10, and 11. The samples will be tested at the study sites using urine dipstick test. Any patient with a positive or doubtful urine pregnancy test must have a negative serum test performed at the central laboratory prior to enrollment or continuation in the study.
- i On Day 2 or prior to any discharge authorization if later than Day 2.
- j Pre-dose samples (may be done along with the safety laboratory samples, when scheduled) during Visits 4 through 7 and Visit 11 and at the approximate time of maximum plasma concentration of both MIN-101 (6 to 8 hours post dosing) and BFB-520 (9 to 12 hours post dosing). PK samples during Visits 8 to 10 should be done pre-dose and 2-4 hours post dosing. A concomitant medication blood sample should be collected coincidental with the PK sample scheduled at the approximate time of maximum plasma concentration of MIN-101 (6 to 8 hours post dosing) during Visits 8 to 10. PK samples should follow the ECG (in triplicate) assessments, when applicable.
- k At each visit, when new medication blisters are dispensed, the patient should start taking drug from the new blisters except at Week 12 (Visit 11) where medication from blisters dispensed during Week 8 (Visit 10) should be used.
-  Patient's drug intake diary should be collected and reviewed, and new diary dispensed with the new medication blisters.
- m Every attempt must be made to complete Week 12 (Visit 11) in case of early termination during the double-blind phase.

TIME AND EV	VENTS S	CHEDUL	LE – OPEI	N-LABE	EL EXT	ENSIC	N PHA	SE									
Study Phase	End of Double- Blind Phase		Open-Label Treatment Phase														
Study Week a	Week 12	Week 12+1 Day	Week 12+2 Days	Week 13	Week 14	Week 15	Week 16	Week 20	Week 24	Week 28	Week 32	Week 36	Week 40	Week 44	Week 48	Week 52 m	EOS/ Week 54 m
Visit Number	11	12	13	14	15	16	17	18	19	20	21	22	23	24	25	26	27
Procedures																	
Hospitalization b		Continuou	S	Xb	Xb												
Safety Assessments																	
Weight and waist circumference c	Х						х	x	х	х	X	Х	х	х	х	x	x
Vital Signs d	X	X	X	X	X	X	X	X	X	X	X	X	X	X	X	X	X
Physical examination e	Х				-		X	X	X	X	X	X	X	X	X	X	X
12-lead ECG (triplicate) f	X	X	X	X	X	X	X	X	X	X	X	X	X	X	X	X	X
Safety laboratories g	X			2			X	X		X		X		X		X	X
HbA1c laboratory test	Х								Х			X				X	X
Urinalysis	X						X	X		X		X				X	X
Pregnancy test (urine)	Х			ас			X	X	Х	X	X	X	Х	Х	X	X	X
RDQ h			Х														
AIMS	Х				t		X	X	X	X	X	X	Х	Х	X	Х	X
SAS and BARS	X			X	X	X	X	X	X	X	X	X	X	Х	X	X	X
Sheehan-STS	X	Х	X	X	X	X	X	X	X	X	X	X	X	X	X	X	X
Adverse events								Contin	uous								
Concomitant medication								Contin	uous								
Other Laboratory Assessments																	

End of Double-**Study Phase Open-Label Treatment Phase** Blind Phase EOS/ Week Study Weeka 12 + 2Week 12 + 148 52m 12 13 14 15 16 20 24 28 32 36 40 44 54m Day Davs 25 Visit Number 11 12 13 14 15 16 17 18 19 20 21 22 23 24 26 27 Pharmacokinetic and concomitant medications X X X X X X X X X X X X X X X X X samplingi **Efficacy Assessments** X Х Х X X X X X X PANSS Х Х Х X Х X X PSP Х X Х X Х X X X X CGI-S X X X X 1 Х Х Х Х X **Study Medication** Administration X X Х X X X X X Х X X X X X X X Dispensek х Х Х X X X Х Х X Х Х Х X Study drug х X Х Х X X х Х X X Х X X X accountability1

NOTE: Patients to be contacted via phone at Weeks 18, 22, 26, 30, 34, 38, 42, 46, and 50 to verify safety and to make sure the patient is doing well and is compliant with study medication.

Abbreviations: AIMS = Abnormal Involuntary Movement Scale; BARS= Barnes Akathisia Scale;

CGI-S = Clinical Global Impression-Severity Scale; ECG = electrocardiogram; EOS = end-of-study; HbA1C = hemoglobin A1c; PANSS = Positive and Negative Syndrome Scale; PSP = Personal and Social Performance; RDQ = Readiness Discharge Questionnaire; SAS = Simpson-Angus Scale; STS = Suicidality Tracking Scale.

Footnotes:

a Visits 14 - 27 may occur  $\pm 2$  days from scheduled visit.

b Patients will be hospitalized starting on the morning of the last day of the double-blind treatment phase (Visit 11) up to Visit 13. Hospitalization on Visits 14 and 15 are at the discretion of the investigator to ensure per-protocol ECG assessment and PK sampling are done. Hospitalization includes admission to a hospital or the utilization of an inpatient facility.

c Patients will be weighed clothed (lightly) and without shoes.

d Vital signs (blood pressure, heart rate, respiratory rate, and oral or aural body temperature) obtained after the patient is resting in supine position for  $\geq$  5 minutes. Vital signs during hospitalization are assessed pre-dose within 30 minutes of dosing, and at about 4 hours post dosing. All other assessments are at about 4 hours post dosing.

e Abbreviated physical examinations at Visits 18, 19, 21, 22, 24 and 25.

f Scheduled ECG recording on Visits 12 through 15 should be done prior to the planned PK sample at pre-dose within 30 minutes of dosing, and at the approximate time of maximum plasma concentration of both MIN-101 (6 to 8 hours post dosing) and BFB-520 (9 to 12 hours post dosing). Scheduled ECG recordings on Visits 16 through 26 should be done prior to the planned PK sample 2-4 hours post dosing after all other assessments have been completed.

g Safety laboratory tests include haematology, serum chemistry (including serum lipid profile, and fasting blood glucose) and prolactin. Patients must fast for 8 hours before the blood sample is taken h On Week 12 + 2 days or prior to discharge authorization if later than Week 12 + 2 days.

 Pre-dose samples (may be done along with the safety laboratory samples, when scheduled) during Visits 12 through 15 and at the approximate time of maximum plasma concentration of both MIN-101 (6 to 8 hours post dosing) and BFB-520 (9 to 12 hours post dosing). PK samples during Visits 16 through 26 should be done pre-dose and 2-4 hours post dosing. One sample will be collected at Visit 27 along with the safety laboratory samples. A concomitant medication blood sample should be collected coincidental with the PK sample scheduled at the approximate time of maximum plasma concentration of MIN-101 (6 to 8 hours post dosing) during Visit 12 through 15, and 2-4 hours after dosing during Visits 16 through 26. PK samples should follow the ECG (in triplicate) assessments.

j At Week 12 (Visit 11), drug dispensed at Week 8 (Visit 10) must be administered.

k At Visits 12 - 25 when new blisters are dispensed, the patient should start taking drug from the new blisters.

 Patient's drug intake diary should be collected and reviewed, and new diary dispensed with the new medication blisters.

m Every attempt must be made to complete both the Week 52 (Visit 26) and EOS/Week 54 (Visit 27) in case of early termination during the open-label extension phase.

